**Serious Reactions:**

- HPA axis suppression (prolonged use)
- Cushing syndrome (prolonged use)
- Hyperglycemia (prolonged use)
- Cataracts (prolonged use)
- Glaucoma (prolonged use)
- Intracranial HTN (prolonged use in pediatric patients)

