### **CONTRAINDICATIONS/CAUTIONS:**

**Duobrii:** 1) Hypersensitivity to drug/class/compound 2) Pregnancy 3) Breastfeeding if applied on nipples 4) Female patients of reproductive potential 5) Pediatric patients 6) Skin infection 7) Photosensitivity 8) Sunburn 9) History of skin cancer

**Bryhali:** 1) Hypersensitivity to drug/class/compound 2) Pediatric patients 3) Skin infection

**Definition of an AE:** Any untoward medical occurrence in a subject administered a pharmaceutical product that does not necessarily have a causal relationship with the treatment. An AE can therefore be any unfavorable and unintended sign (including an abnormal laboratory finding), symptom, or disease temporally associated with the use of a medicinal (investigational) product, whether or not considered related to the investigational medicinal product.

Investigational Medicinal Product (IMP) includes the drug under evaluation and the comparator drug(s) if specified as part of the research objective, given at any time during the study. Medical conditions/diseases present before starting the drug of interest are only considered adverse events if they worsen after starting the drug of interest.

The occurrence of adverse events will be sought by non-directive questioning of the patient at each visit during the study. Adverse events also may be detected when they are volunteered by the patient during or between visits or through physical examination, laboratory test, or other assessments. All adverse events will be recorded in the study database including the following information:

1. the severity grade (mild, moderate, severe)
2. its relationship to the drug(s) of interest (suspected/not suspected)
3. its duration (start and end dates or if continuing at final exam)
4. whether it constitutes a serious adverse event (SAE)

A SAE is any untoward medical occurrence that at any dose:

- results in death
- is life-threatening
- requires inpatient hospitalization or prolongation of existing hospitalization
- results in persistent or significant disability/incapacity

- is a congenital anomaly/birth defect
- is otherwise a significant medical event

This includes any SAEs likely to arise from the trial indication or progression of underlying/concomitant illness(es) (e.g. progression of cancer in oncology trials), unless specified in the protocol as study specific exemptions.

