Any SAE, irrespective of causality, occurring after the subject has provided informed consent and until four weeks after the subject has stopped study participation must be reported unless otherwise stated in the protocol. SAEs occurring after four weeks from ending study participation should only be reported if considered by the Investigator attributable to the exposure to the investigational drug(s) during the trial period. This includes the period in which the study protocol interferes with the standard medical treatment given to a subject, even if study treatment has not yet started (e.g. withdrawal of previous treatment during washout period, change in treatment to a fixed dose of concomitant medication).

**Timelines:** All serious adverse events (SAEs) from interventional clinical trials must be reported by the sites to the Lead PI within 24 hours of occurrence of the SAE and to the site's own IRB as required. The Lead PI will then report to the manufacturer and any other authorities.

**Follow-up reports:** All related SAEs will be followed until resolution or until it is judged to be permanent, and an assessment will be made at each visit (or more frequently, if necessary) of any changes in severity, the suspected relationship to the drug of interest, the interventions required to treat it, and the outcome.

**Pregnancies:** Any occurrences of a pregnancy in a patient (or a patient's partner) during study participation will be collected. All pregnancies will be followed up to determine outcome, including spontaneous or voluntary termination, details of the birth, and the presence or absence of any birth defects, congenital abnormalities, or maternal and/or newborn complications.

Should a temporary or permanent suspension occur, we would report the occurrence to all appropriate authorities.

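### Follow-up to outcome and reassessment of causality are required only for SAEs already judged related; the rule should cover every SAE

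*Combined protocol and SAP*

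**What the plan says.** The relevant rules are in the section headed Contraindications/Cautions, which also holds the AE and SAE definitions and the reporting rules.

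- **Reporting.** The duty covers "Any SAE, irrespective of causality, occurring after the subject has provided informed consent" and runs until four weeks after participation stops. Beyond that, "SAEs occurring after four weeks from ending study participation should only be reported if considered by the Investigator attributable to the exposure".
- **Recording.** "All adverse events will be recorded in the study database", with four items for each event: severity, relationship (suspected or not suspected), duration, and whether it is serious. Duration is given by start and end dates, or by a note that the event was still ongoing at the final examination.
- **Follow-up.** "All related SAEs will be followed until resolution or until it is judged to be permanent". The sentence goes on to require an assessment at each visit, or more often if needed, of "any changes in severity, the suspected relationship to the drug of interest, the interventions required to treat it, and the outcome".

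Two other places bear on relatedness. The Study Design Overview says that treatment-related AEs will be recorded. The section on discontinuation and withdrawal lists, among its reasons, a confirmed AE of grade 3 or higher that is suspected to be related to the test article.

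**The concern.** Reporting is independent of causality, but follow-up is not. Relationship is one of the things the follow-up sentence asks to be reassessed, and an SAE enters that process only if it has already been judged related. The events for which a second look could change the classification from unrelated to related are the ones for which no second look is required.

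Safety is part of the single study objective, alongside efficacy, and a safety account needs an outcome for each SAE it reports. The first judgement may also be provisional. The serious reactions listed for Duobrii are mostly systemic or ocular and are tied to prolonged use. Apart from pregnancy tests, the Schedule of Events shows no laboratory or eye assessment, so such events would come to light clinically.

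**Working it through.** No figure in the plan bears on this point and no arithmetic tests it. The check is to ask, for an SAE first marked not suspected, what each part of the protocol requires.

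| Step | SAE judged related | SAE first marked not suspected |
|---|---|---|
| Reported, from consent to four weeks after participation stops | Yes | Yes |
| Reported, if it occurs later than that | Yes | No |
| Recorded with severity, relationship, duration and seriousness | Yes | Yes |
| Principal investigator informed (Safety Monitoring) | Yes | Yes |
| AEs asked about at each visit (safety text; Appendix A) | Yes | Yes |
| Followed to resolution or until judged permanent | Yes | Not required |
| Relationship, severity, interventions and outcome reassessed | Yes | Not required |

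The last two rows are where the gap lies. I then looked for another provision that might fill it.

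1. *The four recorded items.* They include relationship but set no time or rule for updating it. They do not include outcome or interventions. The duration item lets an event be closed as ongoing.
2. *Questioning at each visit.* This serves to find events. It does not ask for causality to be reconsidered.
3. *Informing the principal investigator.* No re-evaluation step is attached.
4. *The visit schedule.* The last scheduled visit is Week 14. If participation is taken to end there (an assumption), SAEs remain reportable until Week 14 + 4 = Week 18. An SAE in those four weeks that is called unrelated has neither a visit nor a follow-up duty.

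None of these closes the gap. Next, what depends on the causality call:

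- *SAE counts:* nothing within the main reporting window, since reporting there ignores causality.
- *Planned analyses:* nothing. The Data Analysis section covers lesion counts, symptoms, dyspigmentation and patient-reported outcomes, and defines no safety analysis.
- *Any tally of related SAEs in the report:* yes.
- *Outcome data for SAEs called unrelated:* yes.
- *Withdrawal for a grade 3 or higher AE:* yes for that listed reason. The list is stated to be non-exhaustive, and Safety Monitoring separately has the investigator discontinue a subject whose safety is compromised.

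One further inconsistency concerns filtering by relatedness. The Study Design Overview records AEs related to treatment, whereas the safety text records all of them. If the narrower sentence were followed, recording of non-serious AEs would itself depend on the causality call.

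**The case against.** The strongest reply is that the plan already captures what matters. Every SAE is reported within the main window, SAEs go to the Lead PI within 24 hours, all AEs are recorded with an end date or ongoing status, and AEs are assessed at every visit including Week 14 and early termination. Completing an end date means returning to the record after onset, and nothing forbids changing the relationship entry at that point. Assessors are blinded, and the documents give no reason to expect misclassification to favour one arm.

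Most of this stands, and it rules out two stronger readings. A reader might infer that the safety result is fixed by the first causality call. It is not: total SAEs do not depend on that call, and no planned safety result is restricted to related events. A reader might also infer that relatedness can be revised down but never up. The text does not say so. It requires re-review in one class of event and is silent on the other, and silence is not a prohibition.

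Nor do the documents show that the listed serious reactions would be put down to background illness. They name these events as Duobrii reactions, require good general health, and exclude several conditions and treatments that might offer another explanation.

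What the reply does not remove is the restriction itself. Limiting follow-up to related SAEs is a written rule, and a site that follows it exactly may stop following an unrelated SAE before its outcome is known.

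**Conclusion.** The point holds in limited form and is minor. As written, the protocol requires follow-up to outcome and repeated assessment of causality only for SAEs already judged related. SAE counts within the reporting window are unaffected, and no planned analysis is biased. At risk are any related-SAE tally, the outcomes of SAEs called unrelated (most of all after the final visit), and one withdrawal reason that turns on suspected relationship.

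I give no numerical size. The documents state no expected SAE rate and no rate at which causality calls change, and without both any figure would be guesswork. The conclusion rests on reading the follow-up sentence literally and on finding no other provision that requires re-review. A site procedure outside these documents might supply one.

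**What to change.** In the follow-up paragraph, change the opening so that the rule covers *all SAEs, whatever the initial causality judgement*, and leave the rest of the sentence as it stands. Relationship, severity, interventions and outcome are then reassessed for each SAE.

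Reconcile the AE-recording sentence in the Study Design Overview with the one in the safety text, so that the protocol states one recording scope.

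The cost is a short wording change in a protocol amendment, plus follow-up of perhaps one additional event among 30 subjects (a judgement; the documents give no rate). Because resolution may come after the last scheduled visit, some of that follow-up may have to be done by phone after Week 14. No visit, analysis or sample-size change is needed.

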### **Inclusion criteria:**

1. Male or female subject at least 18 years of age
2. Subject is able to provide written informed consent and comply with the requirements of this study protocol
3. Subjects have AKN class I or II (less than 6.5 cm in width)
4. Subjects who are women of childbearing potential (WOCBP) must have a negative urine pregnancy test at screening and must be practicing an adequate and medically acceptable method of birth control for at least 30 days prior to Day 0 and at least 6 months after the last dose of study. Acceptable methods of birth control include intrauterine device (IUD) oral, transdermal, implanted or injected hormonal contraceptives (must have been initiated at least 1 month before entering the study); tubal ligation; abstinence; barrier methods with spermicide. If not of child-bearing potential, subjects must have a sterile or vasectomized partner; have had a hysterectomy, a bilateral oophorectomy or be clinically diagnosed infertile; or be in a menopausal state for at least a year.
5. Subject is judged to be in good general health as determined by the principal investigator.

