## Appendix A.

### Schedule of Events

	Screening	Baseline	W4	W5 c	W8	W12	W14 d	ET
Visit number	1	1 a	2	3	4	5	6	TBD
Informed consent	X							
Medical History	X							
Demographics	X							
Inclusion/Exclusion	X	X						
Concomitant Medications	X	X	X	X	X	X	X	X
Adverse Events	X	X	X	X	X	X	X	X
Pregnancy Test b	X	X	X		X	X		X
Administer IP		X						
Assess IP Compliance			X	X	X	X		
Return IP						X		X
DLQI		X	X		X	X		X
NRS		X	X		X	X		X
AKN severity		X	X		X	X		X
Clinical Photographs		X	X		X	X		X
Clinical Assessment/ Lesion Count		X	X		X	X	X	X
Tape strips (lesional & non- lesional)		X						
Tape strips (lesional only)						X		

- a. If screening is successful, patient will continue into their Baseline visit on same day.
- b. Where applicable, a urine pregnancy test with high sensitivity to HCG will be performed at screening and at all other visits, prior to dosing female participants of childbearing potential with Investigational Product (IP).
- c. Phone call visit
- d. Follow up visit

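### Pregnancy collection appears to end about 24 weeks before the required post-dose contraception period does, and the childbearing-potential wording can take a fertile woman out of testing

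*Combined protocol and SAP*

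**What the plan says.** Four places in the combined protocol and SAP bear on this.

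- **Contraception period.** Inclusion criterion 4 requires women of childbearing potential to practise birth control for "at least 30 days prior to Day 0 and at least 6 months after the last dose of study". The Contraindications/Cautions list for Duobrii includes "2) Pregnancy 3) Breastfeeding if applied on nipples 4) Female patients of reproductive potential".
- **Collection and follow-up.** The Pregnancies paragraph, in the SAE text under Contraindications/Cautions, states that any pregnancy in a patient or partner "during study participation will be collected. All pregnancies will be followed up to determine outcome", and the outcomes named include birth defects. No period after participation is given.
- **Testing and contacts.** Study Design Overview and Appendix A make the Week 14 safety follow-up the last scheduled contact. The pregnancy-test row of Appendix A is marked at screening, baseline, Weeks 4, 8 and 12, and early termination (ET). It is blank at the Week 5 phone call and at Week 14. Footnote b to that row says "a urine pregnancy test with high sensitivity to HCG will be performed at screening and at all other visits", before dosing, for participants of childbearing potential.
- **Who counts as not of childbearing potential.** Criterion 4 continues: "If not of child-bearing potential, subjects must have a sterile or vasectomized partner", and then lists surgical sterility, diagnosed infertility and menopause as further alternatives.

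**The concern.** The protocol sets a post-dose period in which it wants pregnancy avoided, and it wants the outcome of any collected pregnancy known. The duty to follow to outcome attaches only to pregnancies that are collected, and collection is tied to participation. If participation ends at Week 14, a pregnancy that begins later in the contraception period falls under no collection rule, and no contact is planned at which the investigator would hear of it. Information of this kind is hard to recover afterwards.

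The definition in criterion 4 raises a separate question. A partner's sterility does not alter the participant's own fertility. If site staff apply the sentence as written, a fertile woman with such a partner is not of childbearing potential. The screening test in criterion 4, the contraception clause and the footnote b tests all depend on that status.

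**Working it through.** The plan states no figure on this point, so there is nothing to reproduce. The check is timeline arithmetic and a comparison of the passages.

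**Inputs**

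- Planned last dose: Week 12 (12 weeks of treatment in Data Analysis, Primary Endpoint; product returned at Week 12 in Appendix A).
- Contraception period after the last dose: at least 6 months (criterion 4), taken as 26 weeks. Reading it as 24 weeks is the sensitivity case.
- Last scheduled contact: Week 14 (Study Design Overview; Appendix A).
- Assumption: participation ends at that contact. The protocol does not say so.

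**Post-dose period**

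- End of contraception period = 12 + 26 = Week 38.
- Covered after the last dose = 14 − 12 = 2 weeks; 2/26 = 7.7%.
- Uncovered = 38 − 14 = 24 weeks; 24/26 = 92.3%.
- With six months as 24 weeks: end = Week 36; uncovered = 36 − 14 = 22; 22/24 = 91.7%.

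**Other denominators (26-week reading)**

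- Baseline to Week 38: 24/38 = 63%.
- Whole contraception period from 30 days before Day 0: 30/7 = 4.3 weeks, so 24/(38 + 4.3) = 24/42.3 = 57%.

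**Early termination.** If the last dose and the end of participation both fall at the ET visit, up to 26 of 26 weeks are uncovered.

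**Does the SAE rule close the gap?** Any SAE is reportable until four weeks after participation stops, which is Week 14 + 4 = Week 18. After that, an SAE is reportable only if the investigator attributes it to study drug. The SAE list includes a congenital anomaly but not pregnancy. So the rule can bring in a birth defect or another serious event, but not a pregnancy as such. Even if the four-week window were stretched to cover pregnancies, (38 − 18)/26 = 20/26 = 77% of the post-dose period would remain uncovered.

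**Row against footnote.** The Week 14 cell is blank. Footnote b covers every visit other than screening, which on its face includes Week 14, but it also ties testing to dosing, and no dosing is planned then. The two cannot both be followed literally. A Week 14 test would not change the figures above: 24 weeks still follow it.

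**Definition.** Take a fertile woman whose partner is vasectomized. Under the literal text of criterion 4 she is not of childbearing potential. The criterion 4 screening test and the contraception clause apply only to women of childbearing potential, and footnote b has the same limit. Exclusion criterion 5 bars pregnant subjects but prescribes no test. On that reading no test is required of her.

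**The case against.** The case on the other side is substantial in several respects.

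- **A reader might infer that testing simply stops at Week 12.** The documents do not settle that. Footnote b can be read to include Week 14, so what they show is a conflict between row and footnote, not a clean omission.
- **A reader might infer that a pregnancy conceived on treatment would be neither detected nor followed.** That is too strong. The Pregnancies paragraph turns on when the pregnancy occurs, so a conception during dosing arguably falls within it even if recognised later. Adverse events are also sought at Week 14. What such cases may lack is a scheduled means of detection.
- **A reader might call the six months the protocol's risk window and take 92% as a share of risk.** Criterion 4 gives a contraception period without a rationale. The percentage measures calendar time, and the post-dose denominator gives the highest of the three shares. The others are 63% and 57%, so more than half remains uncovered on each.
- **Week 14 as the end of participation is an inference.** This stands. It is the natural reading of the schedule, and the missing definition is part of what needs repair. Consent pages are not among the material reviewed, so they cannot be cited either way.
- **The partner wording looks like a drafting slip.** Probably so. Whether a fertile woman would actually go untested depends on staff applying it literally, but the text as written permits that.
- **The numbers are small.** Thirty participants are planned, 20 on active treatment, and the Introduction describes a disease seen mostly in men. This limits the likely number of cases. It does not remove the mismatch, because women are eligible.

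**Conclusion.** The concern holds as a mismatch between stated rules. If participation ends at Week 14, if six months is about 26 weeks and if the last dose is at Week 12, about 24 of 26 post-dose weeks (92%) have neither scheduled contact nor pregnancy collection. For a participant who terminates early it may be all 26. The SAE rule is a partial backstop for birth defects and other serious events only.

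Two further points stand on the text alone: the Week 14 test cell conflicts with footnote b, and criterion 4 treats a partner's sterility as a property of the participant.

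The documents do not show that six months is the right contraception period or that drug-related risk lasts that long. Nor do they show that any participant will in fact be dosed untested. The expected number of affected participants is small, and no endpoint or efficacy analysis depends on this.

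**What to change.** 1. In the Pregnancies paragraph, make the collection period run to the end of whatever post-dose contraception period criterion 4 retains, and state how later pregnancies will be ascertained.
2. Define the end of study participation, both for completers and for those who leave at an ET visit.
3. Reconcile the Week 14 cell of the Appendix A pregnancy-test row with footnote b, so that the two give one testing schedule.
4. Reword criterion 4 so that a partner's sterility or vasectomy does not classify a participant as not of childbearing potential.

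Which contraception period and testing schedule to keep is for the sponsor and investigator to decide; the request here is that the sections agree.

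The cost is amendment wording, a longer reporting tail and a later contact for the few women enrolled. The efficacy analysis does not change.

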### **DISCONTINUATION OF TREATMENT AND WITHDRAWAL OF SUBJECTS:**

The reasons why a subject may discontinue or be withdrawn from the study by the investigator include, but are not limited to the following: subject request, protocol violation, loss to follow up, subject non-compliance, study termination by investigators, and a confirmed grade 3 or higher adverse event, which is suspected to be related to test article administration.

Participants will be given a standard calendar dosing diary that will allow them to place checkmarks each day that study drug was taken. Investigators will assess diary at all in-person visits (weeks 4, 8, and 12). Subjects will be terminated from study if they do not maintain  $\geq 50\%$  dosing compliance.

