Enrolled participants will be instructed to apply placebo (n=10) vs. active (n=20) to affected area of the occipital scalp for 4 weeks once a day (label use). Each application will be approximately 1g. Following the 4 weeks, participants will be instructed to increase application to twice daily (BID; off-label; at least 8 hours apart) for one week. Investigators will conduct a phone visit on week 5 to discuss any potential side effects with this increased dose. If tolerated, this BID regimen will be carried throughout the length of the study. If BID is not tolerated (if irritation occurs), then Bryhali will be used as a “rescue treatment” once daily for 1 week before the subject returns to BID treatment with Duobrii. If irritation recurs, subjects will be instructed to alternate Duobrii and Bryhali (ie Duobrii BID one day, followed by Bryhali QD the next day, Duobrii BID the next, and so on). Alternating topical steroid use and stepping down topical steroid strength have been known to reduce lesion count in AKN. If irritation continues to persist, then participants will be instructed to use Bryhali QD for five days a week and Duobrii BID two days a week. If participants still experience irritation with this regimen, then subjects will be transitioned entirely to Bryhali QD for the remainder of the study. In case of clearance earlier than the end of the study, participants will be instructed to continue their respective regimen to completion of the study. Gentle hair care regimen will be recommended for duration of the length of the study; with unscented shampoo & conditioner (such as Head & shoulder) and Vaseline to scalp as moisturizer to minimize risk of contact dermatitis. In addition, patients will be instructed to postpone any form of hair coloring or chemical hair processing until after the study is over.

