Participants will be followed with visits scheduled at baseline, 4 weeks, 8 weeks and 12 weeks. At each visit, participants will complete surveys regarding the severity of AKN's associated symptoms (pain, pruritus, burning etc.) as well as the dermatology quality of life index (DLQI) and numerical rating scale (NRS) surveys (Appendix B&D). In addition, photographs will also be obtained for global assessment and lesion count will be performed. The investigator will assess the treatment area for any dyspigmentation and document the % area affected within the treatment area at each visit. Tape strips will also be collected from lesional (occipital scalp) and non-lesional (frontal scalp) at Baseline and Week 12. There will be a phone call visit at week 5 to assess tolerance of medication increase and a safety follow-up visit at Week 14. Statistical analysis will be performed. Throughout the length of the study, any adverse events (AEs) related to the treatment will be recorded.

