## **Primary Endpoint**

The primary analysis for the primary endpoint will test for a reduction in lesion counts after 12 weeks of treatment. We will apply the two-sided Wilcoxon test to assess the significance of the difference between pre- and post-treatment median numbers of lesion counts. The secondary analysis will compare the reduction in lesion counts between active and placebo groups after 12 weeks. For this purpose, we will apply the Z-test to verify the hypothesis that the proportions of patients with reduced AKN lesions differ between active and placebo groups. A more comprehensive analysis will adjust a generalized linear mixed-effects model, based on Poisson distribution, including time and treatment group as fixed factors and a random intercept for each subject. This model will include the whole time-course and contrasts of interests will be estimated.

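### The 50% diary-compliance rule ends study participation, not just treatment, so a failure found at week 4 or 8 needlessly gives up the week-12 lesion count

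*Combined protocol and SAP*

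**What the plan says.** The rule is in the section on discontinuation of treatment and withdrawal of subjects: "Subjects will be terminated from study if they do not maintain" dosing compliance of 50% or more. It is mandatory, and what ends is the study. On timing, the same section says "Investigators will assess diary at all in-person visits (weeks 4, 8, and 12").

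Under Data Analysis, Primary Endpoint, "The primary analysis for the primary endpoint will test for a reduction in lesion counts after 12 weeks of treatment", by a two-sided Wilcoxon test of pre- against post-treatment counts. The secondary analysis, also at 12 weeks, is a Z-test of whether "the proportions of patients with reduced AKN lesions differ between active and placebo groups". A Poisson mixed model follows: "This model will include the whole time-course and contrasts of interests will be estimated". The section defines no analysis set, gives no missing-data rule, and does not say whether a count taken at early termination may replace the week-12 count.

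The Study Design Overview sets the visits: "Participants will be followed with visits scheduled at baseline, 4 weeks, 8 weeks and 12 weeks", plus "a safety follow-up visit at Week 14". Appendix A marks a lesion count at baseline, weeks 4, 8, 12 and 14, and at early termination (ET). The overview also contains a stepwise reduction to Bryhali for irritated subjects, introduced by the condition "If BID is not tolerated (if irritation occurs"). Sample Size Considerations allows for 30% dropout and does not say whether compliance terminations are counted in it.

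**The concern.** Compliance is measured after randomisation and may depend on treatment, for instance through irritation. Removing subjects because of it means the week-12 Z-test compares two groups that were partly selected after allocation, so the comparison no longer has the full protection of the 2:1 randomisation. The pre-post Wilcoxon test makes no between-arm comparison; for it, the consequence is a smaller, selected sample.

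Other dropout does similar harm. The difference is that this loss is imposed by the protocol on people who may be willing to attend, so it can be avoided. With 20 and 10 subjects, a handful of missing counts can decide how the between-arm result reads, and counts that were never taken cannot be recovered at analysis.

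**Working it through.** **1. What each diary check costs.** This sets the withdrawal rule against the visit schedule.

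| Failure found at | Lesion counts held | Week-12 count | Scheduled in-person visits given up |
|---|---|---|---|
| Week 4 | baseline, week 4/ET | lost | weeks 8, 12, 14 (3) |
| Week 8 | baseline, week 4, week 8/ET | lost | weeks 12, 14 (2) |
| Week 12 | baseline, weeks 4, 8, 12 | need not be lost; scheduled at the same visit | none before the primary time point |

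An ET count at week 4 comes at the end of the once-daily phase, before twice-daily dosing begins, so it is a poor stand-in for week 12. The mixed model can use the counts taken before exit. It supplies no week-12 value to the Wilcoxon test or the Z-test.

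**2. The plan's own figure.** Inputs from Sample Size Considerations: mean baseline 15, reduction 35%, SD 7, one-sided 5%, 80% power, 30% dropout.
- Difference = 0.35 × 15 = 5.25; standardised, 5.25/7 = 0.75.
- Paired t power (noncentral t), with sample size scaled by the Wilcoxon relative efficiency 3/π = 0.955: 13 completers give 79.9%, 14 give 82.7%. So 14 are needed.
- 14/(1 − 0.30) = 20. The stated n=20 reproduces.

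The allowance is thus a matter of numbers: 14 of 20 active and 7 of 10 placebo completers. It says nothing about who those completers are. If compliance terminations fall within it, the 82.7% stands. If they come on top, 13 completers give 79.9% and 12 give 76.6% on the plan's one-sided basis.

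**3. Bounds on the all-randomised difference in proportions.** Let a active and b placebo subjects lack a week-12 count.
- Lower bound: every missing active subject not reduced, every missing placebo subject reduced. Upper bound: the reverse.
- Width = a/20 + b/10. One active subject adds 1/20 = 5 points; one placebo subject adds 1/10 = 10 points.

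**4. Illustration.** Assumed, because the documents give no removal rate: 10% removed per arm, that is 2 active and 1 placebo. Responder counts are also assumed. The test is the pooled Z, z = (p_a − p_p)/√[p̄(1 − p̄)(1/n_a + 1/n_p)], taken two-sided because the Primary Endpoint section words the hypothesis as a difference.

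| Case | Active | Placebo | Difference | z | p |
|---|---|---|---|---|---|
| Completers | 15/18 | 4/9 | 39 points | 2.09 | 0.037 |
| Lower bound | 15/20 | 5/10 | 25 points | 1.37 | 0.17 |
| Upper bound | 17/20 | 4/10 | 45 points | 2.54 | 0.011 |

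The width is 2/20 + 1/10 = 20 points, which agrees with 45 − 25.

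**The case against.** Several points on the other side have force.

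- **Irritated subjects are stepped down, not left to fail.** The regimen moves through a week of Bryhali, alternating days, a five-and-two-day split, and finally Bryhali alone. Together with a lenient 50% threshold, this should reduce irritation-related non-compliance. It does not remove it: the steps are tied to intolerance of twice-daily dosing, so irritation in the first four weeks is not clearly covered. Non-compliance through perceived lack of benefit is plausible, but the documents do not discuss it.
- **The bounds apply to any missing count.** That is so; they do not measure how many this rule removes. Part of the fragility is simply the sample size: one fewer active responder (14/18 versus 4/9) moves p from 0.037 to 0.083 with no change in removals.
- **The real gap is the absent missing-data rule.** The plan neither enters the ET count in the two tests nor bars it, and a rule would help. But a rule can only handle a missing week-12 count; keeping the visit prevents it.
- **The sponsor may want the effect in adherent users.** No such aim is stated. If it is wanted, that subset can still be analysed after everyone has been followed.

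A reader might infer that the results would describe only subjects who kept applying product. The text does not support that: the rule retains anyone missing up to half their doses, and someone who stops after week 8 can still supply a week-12 count. A reader might also charge the whole 30% dropout allowance to this rule. The plan gives 30% as a maximum for dropout and lists several other reasons for leaving, so that would overstate it.

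**Conclusion.** The point holds. A mandatory rule forgoes week-12 lesion counts that could have been collected, whenever a compliance failure is found at week 4 or 8. The ET count and the mixed model soften this without curing it, and the dropout allowance covers numbers rather than comparability.

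The size is 5 points of uncertainty per missing active subject and 10 per missing placebo subject in the all-randomised difference. In the illustration that is enough to span p=0.011 to p=0.17. The bounds are extremes, and the illustration rests on an assumed removal rate and assumed responder counts. They also take the Z-test to be run on subjects with an observed week-12 count, since the plan states no alternative.

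The documents do not support a claim that the rule favours Duobrii, or favours placebo; the direction of any bias is unknown. Nor do they support a claim that the pre-post Wilcoxon test loses randomised comparability, because it never had a between-arm contrast to lose. The change should be made, but its practical importance depends on a removal rate nobody can state in advance.

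**What to change.** Amend the discontinuation section so that compliance below 50% ends study drug only. Keep these subjects on whichever of the week 8, 12 and 14 visits and lesion counts remain, unless they withdraw consent, and record any other AKN therapy started after stopping. Analyse all randomised subjects in their assigned arm, with the subset at 50% compliance or better as a sensitivity analysis. For anyone who still leaves early, enter the ET count in the mixed model at its actual time and report best-case and worst-case bounds beside the Z-test.

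The cost is amendment wording plus visits already in the schedule: three for a subject stopped at week 4, two for one stopped at week 8. The real downside is that including poor adherers may shrink the estimated effect and lower power in a 30-subject trial, so no gain in power should be expected from the change.
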